#### **4.2. Payment for Participation**

Participants will be paid \$60 following completion of the two-part baseline assessment and will be paid additional \$20 if part-two of the baseline assessment is completed within 7 days of part-one. Participants will also be paid \$40 following the completion of each follow-up assessment and will be paid an additional \$40 following the completion of the last follow-up assessment (whether the last follow-up occurs at 6 months, 9 months, or 12 months following the baseline assessment) if all prior follow-ups are completed. This would provide a maximum total compensation of \$320 for individuals completing 1, 3, 6, 9, and 12 month follow-ups; it would provide a maximum total compensation of \$280 for individuals completing 1, 3, 6, and 9 month follow-ups; and a maximum total compensation of \$240 for individuals completing 1, 3, and 6 month follow-up assessments. Payments will be made securely by check, gift card, cash, or electronically (Department payment cards will be used as the mechanism for purchasing e-gift cards from Amazon).

### **5. REPORTABLE EVENTS**

#### **5.1 Adverse Events**

All adverse events will be identified and reported to [name], who will be responsible for the timely reporting of adverse events to the required oversight entities. Such events will be documented in the adverse event log maintained by the study team. All adverse events will also be communicated to the IRB in the form of continuing reviews, and an annual report will be submitted to the NIAAA project officer summarizing adverse events. Adverse events that are determined to be unanticipated, study-related, and serious will be reported by [name] to the IRB, and the NIAAA Project Officer within 48 hours of discovery. All adverse events will be followed up by [name] in a timely way as to prevent any risks to participants, in coordination with the IRB.

#### **5.2 Suicidality**

The PHQ-2 and Standardized P4 Screener measure may result in the discovery of suicidal thoughts or behavior. Specifically, if depressed mood or lack of interest or pleasure is identified on the PHQ-2, it triggers administration of PHQ-9 item #9. If the subject endorses thoughts of self-harm on item #9, then the standardized P4 screener is administered which categorizes individuals into “minimal risk”, “lower risk”, and “higher risk.” If a subject is determined to be at “lower risk” or “higher risk” on the P-4, following the call, the assessor conducting the assessment will contact the PI ([name]) or another qualified investigator on the research team who will review the assessment and determine if a follow-up call with the subject may be beneficial to promote safety. If this is the case, [name] or another qualified investigator will seek to follow-up with the subject as needed by telephone to obtain further assessment and assist them as necessary. Typically, subjects deemed at “higher risk” would warrant such a follow-up call, unless there are mitigating

circumstances to suggest it is not clinically indicated, whereas subjects deemed at “lower risk” would be less likely to require follow-up. There are a broad range of potential responses to address risk including further assessment by phone, making a plan to reach out for additional support or formal treatment, and, in rare circumstances, initiating an emergency intervention (e.g., calling 911).

## **6. RISK/BENEFIT ASSESSMENT**

### **6.1. Risks to Subjects**

Risks include that the subjects will be identified as participants in an alcohol treatment study, inadvertent breach of confidentiality concerning drinking behavior, or that assessments, the CBT-TE, or the control intervention may temporarily adversely affect an individual’s well-being (e.g., experience discomfort while discussing the consequences of alcohol use).

### **6.2. Benefits to Subjects**

Benefits to participants include the possibility of receiving an intervention, at no cost, with preliminary evidence of efficacy to promote entry into alcohol-related care.

### **6.3. Alternatives to Participation**

The alternative to participation is not to participate.

## **7. CONFIDENTIALITY OF DATA AND INFORMATION STORAGE**

With respect to confidential data collection, all project data will be collected by trained research interviewers using IRB approved data collection instruments. In addition, research interviewers and interventionists will receive on-going supervision through the course of the project. All data will be stored in locked file cabinets and password protected databases and will be accessible only by appropriate research personnel. All subject data will be identified by a unique number. Subject identifiers (e.g., name, address, telephone number) will be stored separately from research data and linkable through a unique identification number. The control and treatment interventions to be used in the project have been implemented in prior research without causing serious harm (Stecker et al., 2012). All study personnel will receive mandatory education in human subjects’ protection. All data will be used for research purposes only, and will not be revealed without the participants’ written consent unless to protect individuals immediate safety. All paper data will be kept in locked files in a locked study office. Computerized data will be stored in databases on a secure, password protected server that is regularly backed up. As an added protection, NIH funded studies are covered by a Federal Certificate of Confidentiality.

We will share data with other researchers and use widely used measures that will facilitate harmonization with other research. However, the data sharing agreement involves sharing only de-identified data with other investigators and the use of data-sharing agreements that provide for: (1) a commitment to using the data only for research purposes and not to identify any individual participant; (2) a commitment to securing the data using appropriate computer technology; and (3) a commitment to destroying or returning the data after analyses are completed.

All research and clinical information obtained is kept confidential unless the subject is an immediate danger to him/herself or to others. Subject well-being will be monitored throughout the study. If the clinical information obtained in the course of research assessments pertains to patient safety (e.g., intent to harm one’s self or others) then, to promote safety, confidentiality will not be maintained, and appropriate treating professionals will be informed. During crisis situations, this clinical information may be provided to other clinicians (or family members) in order to facilitate appropriate treatment and minimize the risks of self-harm or harm to others. This information may include the subject’s medical history, financial and social resources, and history of suicidal behavior, if known.

Confidentiality is the ethical and/or legal right that information, such as research data, will be held secret and safeguarded from disclosure unless consent is provided permitting disclosure.

## 8. DATA ANALYSIS AND DATA MONITORING

### 8.1. Planned Statistical Analysis

What are the statistical/analytical methods to be used for the collected research data and to meet the goals of any specific endpoints that will be analyzed?

### 8.2. Data and Safety Monitoring

1. *The DSM plan must designate an experienced, qualified professional (usually the PI) who can distinguish a serious adverse event (SAE) from a non-serious adverse event (AE).*

PI Response: [name], contact PI of this study, will review all adverse events, and decide if they are serious or non-serious adverse events. As needed, he will consult with multi-PI [name] on these determinations. [name] has the expertise to make these judgments and will be available to make any necessary decisions within the reporting timeframe.

2. *The DSM plan must indicate that serious adverse events will be reported to the local IRB and to the NIAAA project officer within 48 hours.*

PI Response: Any reportable serious adverse events experienced in this study (i.e., those that are serious, unanticipated, and study related) will be reported to the University of Rochester Medical Center (URMC) IRB, and to the NIAAA project officer ([name]) within 48 hours of the event.

3. *The DSM plan must indicate that an annual report will be submitted to the NIAAA Project Officer summarizing all adverse events.*

PI Response: An annual report will be submitted to the NIAAA Project Officer summarizing all adverse events.

4. *The DSM plan must specify that female subjects who are pregnant, nursing, or not using effective methods of birth control will be excluded from studies involving the administration of alcohol and/or drugs.*

PI Response: N/A

5. *The DSM plan must indicate that trained personnel will be present or on call when human laboratory studies of alcohol or other drug intake are conducted.*

PI Response: N/A

6. *For studies in which alcohol is administered, the DSM plan must indicate that NIAAA guidelines for the administration of alcohol will be followed. These guidelines can be found at the following web address: <http://www.niaaa.nih.gov/extramural/job22.htm>*

PI Response: N/A

7. *If the study has a follow-up phase, there must be a specific plan for referral to treatment during follow-up of any respondent requiring additional intervention due to significantly increased alcohol consumption or serious psychiatric/medical symptoms.*

PI Response: This study will follow participants for 12 months. Any information that we

collect at any point in the study that suggests that a participant may require or could be helped by it will be referred to treatment as indicated.

8. *The DSM plan must indicate that all adverse events during follow-up will be reported (SAEs within 48 hours) to the IRB and NIAAA.*

PI Response: All adverse events during follow-up will be reported to the URMC IRB, and to NIAAA.

9. *The DSM plan must briefly describe the procedures for data quality assurance and confidentiality.*

PI Response: Procedures will be in place to assure data quality and participant confidentiality. The procedures for data quality are: a) Adhere to CONSORT guidelines for conducting and reporting two-group parallel RCT's (Begg et al., 1996; Moher et al., 2001; Schulz et al., 2011). b) Regular meetings of the multi-PIs and the project staff to review any concerns regarding participant data. c) All data will be entered by trained project staff and will be double checked for accuracy. d) Assessment data will be entered into REDCap (Research Electronic Data Capture), a widely software toolset and workflow methodology that was created specifically around HIPAA-Security guidelines. The procedures for confidentiality are: a) Respondent records [questionnaires, computer data] will be labeled by code number only. b) All research personnel will be trained in procedures in assuring confidentiality, and only trained personnel will have access to subject records. c) Individual data will never be presented. The data will be analyzed and reported only in terms of group outcomes. d) The project will be covered by a Federal Certificate of Confidentiality.

10. *Phase III clinical trials must have an independent data and safety monitoring board.*

PI Response: N/A

ClinicalTrials.gov Cover Page – Statistical Analysis Plan

Title: Talk Therapy by Phone to Promote Treatment for Alcohol Problems

NCT number: NCT03758274

Date: July 2, 2018

Statistical Design and Power

[figure not shown]
Sample size calculation: Power Analysis: Our estimates of statistical power and required sample size were informed by the prior study by Stecker and colleagues (8). In this study, the control group rate of treatment use was 12%, and the treatment group rate was 31%, representing a 2.58 times increase. Given that this study was the first test of the intervention in a sample with elevated alcohol use, we chose a more conservative effect size of a 2.0 times increase in treatment use to account for the potential uncertainty in the generalized effect size and to buffer against the potential for regression to the mean across conditions. Using this effect size and base rate of treatment use, a sample of 450 participants (~225 in each condition) would provide power of 0.89 at a two-tailed alpha level of 0.05. This sample size allows for a loss of up to 20% of participants at follow-up while maintaining power at 0.81, and serves as a further buffer against the downward bias associated with intention-to-treat principles. In the table, we have provided power estimates using both these conservative settings (i.e., smaller than expected effects with high attrition) and more likely scenarios. We were further conservative in our approach by utilizing a two-tailed alpha level, as there is little reason to anticipate an iatrogenic effect in the current study. Use of a one-tailed alpha (i.e., testing if treatment use is higher in the intervention condition than in the control rather than simply whether they are different), provides power of 0.80 to find an effect as small as 1.75 times difference, with power of 0.73 retained if 20% attrition were observed.

The baseline sample size of 450 affords us the ability to detect bivariate associations between treatment use and alcohol consumption outcomes at the 6-month follow-up as small as 0.14 with power of 0.85 (0.15 with power of 0.85 and 10% participant attrition; 0.16 with power of 0.85 and 20% participant attrition). We used MacCallum, Browne, and Cai's (110) method for deriving power estimates for the fit of nested SEMs (111), which, in this case, involves comparing freely estimated models to those without certain paths (i.e., models without residual direct effects of treatment condition on alcohol consumption outcomes, which imply full mediation). Following common cut points for model fit (112), we assumed a RMSEA of 0.05 for the well-fitting model and 0.10 for a poor fitting model. With a sample size of 450 and our variables of interest, we have power of approximately 0.87 to detect significant changes in fit associated with eliminating paths from the model.

Randomization procedures. Baseline assessments are performed by the University of Rochester Medical Center (URMC) based study team. After the baseline assessment, subjects will be randomly assigned with equal allocation to Cognitive Behavioral Therapy for Treatment Engagement (CBT-TE) or the control condition. The randomization plan will be generated by [name], co-I and study statistician, using an established SAS macro. Only [name] will have access to the treatment assignment prior to a subject being randomized, eliminating the possibility of selection bias. The randomization will be implemented via a REDCap module. The randomization plan will also include blocking to ensure that an equal number of subjects have been assigned to the two treatment groups after a certain number of subjects have been enrolled (block size). Only [name] will be aware of the block size used.

Statistical Power assuming a baseline sample of 450 participants, 12% treatment use in the control condition, and two-tailed α level of 0.05

Treatment Use % in the Intervention Condition	Attrition Proportion	Statistical Power
24% (2.00X increase)	10%	0.86
27% (2.25X increase)	10%	0.96
30% (2.50X increase)	10%	0.99
24% (2.00X increase)	20%	0.81
27% (2.25X increase)	20%	0.94
30% (2.50X increase)	20%	0.98

Following baseline assessment, the URMC based research staff member who performed the assessment will inform the subject that he/she will be contacted and informed of his/her study assignment within one business day by a member of the Medical University of South Carolina (MUSC) based study team. Upon ending the call, the URMC based research staff member will inform the MUSC team that a new subject has been enrolled and requires randomization and follow-up within one business day, with the subject number provided. The MUSC based research assistant will access the subject's assessment information and contact information through REDCap with a username and password, and subsequently access the module to receive the subject's treatment assignment. Within one business day, the MUSC research assistant will contact the subject and inform them of their treatment assignment (CBT-TE or control), following a script for informing subjects of their condition. For control subjects, the research assistant may perform the control intervention (i.e., read the subject an NIAAA pamphlet) immediately if the subject wishes, or schedule the control session. Subjects assigned to the CBT-TE therapy condition will be provided an appointment with a therapist within one week. The strategy to have the randomization assignment accessed by the MUSC based team, and communicated to subjects by the MUSC based team, allows the URMC based research staff to remain blinded to treatment assignment. This strategy is facilitated by the unique roles played by URMC (data management, recruitment, baseline assessment, follow-ups) and MUSC (provision of CBT-TE and control interventions). Accordingly, the same URMC research staff member who performed the initial assessment will be able to perform follow-ups, advantageous to maintaining rapport with subjects. Subjects will be instructed not to communicate their treatment group during follow-up assessments.

Statistical Analyses: Overview: We will use structural equation models (SEM) in Mplus 7.11 (99) to accomplish our specific aims. SEM is a flexible analytic method that enables us to examine the main effects of the intervention on alcohol treatment use (**Aim 1**) and alcohol use outcomes (**Aim 2**), as well as mediation pathways to alcohol use outcomes through treatment use (**Aim 3**).

[figure not shown]

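### The SAP says selection bias is eliminated, but the MUSC assistant sees baseline data before drawing each allocation, learns arms as they accrue and has no fixed draw order; the likely bias is small and cheap to remove.

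*SAP*

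**What the plan says.** All of this is in the SAP under Randomization procedures. The statistician generates a blocked 1:1 list, and a REDCap module releases the assignments. Concealment is argued from who can see the list: only the statistician "will have access to the treatment assignment prior to a subject being randomized, eliminating the possibility of selection bias". The statistician alone knows the block size. Balance is to be reached "after a certain number of subjects have been enrolled (block size"; no value is given, and the text does not say whether sizes vary.

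The workflow then runs as follows. URMC staff complete the baseline assessment and notify MUSC that an enrolled subject needs randomization. "The MUSC based research assistant will access the subject's assessment information and contact information through REDCap with a username and password". Only after that step does the assistant draw the arm from the module. Within one business day the assistant tells the subject the arm. For control subjects "the research assistant may perform the control intervention" at once; CBT-TE subjects "will be provided an appointment with a therapist within one week". URMC staff, who also do the follow-ups, stay blinded.

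Under Primary analyses and Preliminary analyses, baseline drinks per drinking day (DDD) and percent days abstinent (PDA) enter all models. Age, sex and AUD symptom count enter only if the arms differ at p < 0.05.

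**The concern.** Hiding the list protects an allocation only if the person at the point of assignment cannot anticipate it, or cannot act on the anticipation. Here the MUSC team learns arms as they accrue, and blocking forces the arms back towards balance, so the running count carries information about the next draw. The assistant also reads the subject's baseline data before drawing. If two subjects are waiting, nothing in the SAP says which is drawn first. Someone who expects the next slot to be CBT-TE could give it to the subject who looks likelier to enter treatment.

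At stake is the Aim 1 comparison of treatment use, on which the study is powered. Steering of this kind would create a difference between the arms that is not caused by CBT-TE, and the stated guarantee would be wrong for the step that assigns the arm.

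**Working it through.** **Design figures.** The documents give no figure for block size or predictability. The planned contrast is 12% against 24% treatment use, 225 per arm, two-sided alpha 0.05, stated power 0.89 (SAP, Sample size calculation). With continuity correction: z = [(0.12 − 1/225) − 1.96 × √(2 × 0.18 × 0.82/225)] / √((0.12 × 0.88 + 0.24 × 0.76)/225) = (0.1156 − 0.0710)/0.0358 = 1.245, so power is 0.894. The stated figure reproduces, and the yardstick for bias is a 12-point difference.

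**How predictable is the next arm?** Assume fixed 1:1 blocks of size 2m.

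- Always naming the arm with fewer subjects so far needs no knowledge of the size. Share correct = [m + 2^(2m−1)/C(2m,m) − 1/2]/(2m). For m = 2: (2 + 8/6 − 0.5)/4 = 0.708.
- If the size were known or worked out, the share of allocations that are certain = 1/(m+1). For m = 2: 1/3, or 150 of 450.

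| Assumed block size | Correct guess, size unknown | Certain, size known | Certain, of 450 |
|---|---|---|---|
| 2 | 75% | 50% | 225 |
| 4 | 71% | 33% | 150 |
| 6 | 68% | 25% | 112 |
| 8 | 67% | 20% | 90 |
| 10 | 65% | 17% | 75 |

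Simple randomization would give 50% correct guesses and none certain.

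**What could be done with the guess?** At the allocation step the assistant cannot choose who enters, only which of two waiting subjects is drawn first. (Withdrawal and replacement after randomization, Protocol 3.2, is a separate matter and is not counted here.) Simulation with 450 subjects, 4,000 trials per setting and no true effect. Assumptions: two equally common prognostic groups with 6% and 18% treatment use; a drawer who recognises the group perfectly and always acts on the running count; unadjusted analysis.

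| Block | Share of draws with a second subject waiting | False risk difference (points) | Type I error |
|---|---|---|---|
| 4 | 10% | 0.2 | 0.053 |
| 4 | 25% | 0.3 | 0.047 |
| 4 | 50% | 0.7 | 0.052 |
| 4 | 100% | 1.4 | 0.072 |
| 6 | 50% | 0.4 | 0.054 |
| 6 | 100% | 1.0 | 0.062 |
| 2 | 50% | 1.5 | 0.080 |
| 2 | 100% | 3.0 | 0.163 |

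Simulation error on a rate near 0.05 is √(0.05 × 0.95/4000) = 0.003, so up to 50% waiting the rates for blocks of 4 cannot be told from 0.05.

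**A second set of assumptions.** Steering only at slots that are certain, 10 to 30% of them with a second subject waiting, propensity SD 0.8 on the logit scale, mean treatment use 12 to 18%. With perfect ranking of propensity, blocks of 4 to 8 give about 0.1 to 1.0 points; blocks of 2 at 30% waiting give 1.3 to 1.9. If what the assistant sees correlates only 0.3 with propensity (12% use), blocks of 4 to 8 give 0.0 to 0.2.

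**The case against.** The case for the plan is substantial.

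- **Entry into the trial is closed to the drawer.** Recruitment and baseline assessment are done by blinded URMC staff before MUSC is told of the subject. This stands. A reader might infer that the drawer can influence who is enrolled; the SAP workflow rules that out.
- **The block size is concealed and may vary.** A reader might infer one fixed size, and hence that a third or so of allocations are known with certainty. The singular wording suggests a fixed size but does not state it, and a public document may properly withhold block details. The certainty column above is therefore conditional. The better-than-chance guess is not: it needs no knowledge of the size and stays at 68 to 69% for the varying mixes in the fix below.
- **More than one person may draw.** That a single assistant sees every allocation is an inference; the text also speaks of a member of the MUSC team. Guessing is weaker if knowledge is not shared.
- **The scheduling difference is not a motive for bias.** Immediate control sessions against a CBT-TE appointment within a week could lead staff to time draws by workload. That is unrelated to prognosis and matters only if subjects change places.
- **Planned adjustment helps.** Baseline DDD and PDA are in every model, so steering on drinking is largely covered. The IMPASS treatment beliefs are taken immediately before the session (Protocol 4.1a, table footnote), hence after the draw. Other baseline measures in that table, such as the TPB, INDUC and WHOQOL-BREF, are not named as covariates, so adjustment is incomplete.
- **Steering would have to be deliberate.** True, but a claim that the possibility is eliminated is a claim about what the procedure allows.

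**Conclusion.** The stated property does not hold. The procedure lets someone with an informed guess at the next arm see baseline data and choose the order of draws. Concealing the block size does not remove that guess.

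The practical size is small: about 0 to 1 percentage point on the Aim 1 risk difference for blocks of 4 or more with up to half of draws having a second subject waiting. It is larger only for blocks of 2, or if nearly all draws have one waiting. These figures assume a drawer who knows the running count and always acts on it, mostly with perfect reading of prognosis and with no adjustment, so they lie towards the upper end. The block size and the frequency of waiting subjects are not in the documents.

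A reader might go further and infer that Aim 1 is materially compromised. The documents do not support that. This is a free improvement to the procedure and a correction of wording, not a threat to the trial's conclusion.

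**What to change.** In the SAP, Randomization procedures:

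1. Require that each allocation be drawn in the order in which URMC flags subjects as ready, and before MUSC opens the assessment record. This closes the route. A written rule is enough; whether REDCap can automate it is not stated in the documents.
2. State that the result is visible only to MUSC. URMC handles data management and follow-up, so access rights must keep the assignment from the blinded assessors.
3. Replace the claim of elimination with a description of these safeguards.
4. Optionally, use randomly varying block sizes. In simulation, with a guesser who knows the set of sizes, certain allocations fall from 33% (fixed 4) or 25% (fixed 6) to about 6% (mix of 4 and 6) or 2% (mix of 4, 6 and 8). Correct guesses hardly move: 71% and 68% become 69% and 68%. This supplements item 1 and cannot replace it.
5. Reconcile the timing. Protocol section 1 places randomization after part one of the baseline assessment and the session right after part two; the SAP says only that randomization follows baseline. The order of draw, part two and session should read the same in both.

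The cost is a few sentences, an access setting and, for item 4, new parameters in the SAS macro with a final imbalance of at most half the largest block. Sample size and power are unchanged. If recruitment has ended, correct the claim and report the procedure actually used.
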